#### **5. PARTICIPATING SITES**

The study will be conducted, inclusive of screening, enrolment, assessment and intervention delivery, in-person at one or more sites listed below or via a secure online platform such as Zoom . The University of Sydney has software licenses to all 3 platforms. Recruitment will be conducted at Cana Farm and other facilities which are part of Cana Communities in the greater Sydney area via in-person, online or telephone. Screening and medical assessments will be conducted privately at the University of Sydney or via a secure online platform with additional contact by telephone or email as needed.

**6. RESEARCH PLAN / STUDY DESIGN**

**6.1. TYPE OF STUDY**

6-month translational study.

**6.2 POPULATION / SAMPLE SIZE INCLUDING POWER CALCULATION**

We will recruit men and women who have had any interaction with Cana Communities. This may be via provision of services, general inquiries or individuals who have been identified as suitable for the CanaCare Clinic study by Cana Communities staff and volunteers.

Our sample size calculation is based on a pilot randomised controlled trial in a non-clinical adult population, who were randomly allocated to one of two positive psychology interventions. Effect size and sample size estimates based on the changes in the Oxford Happiness Questionnaire following each intervention are summarised below.

Intervention	Pre (mean)	Post (mean)	Mean difference	Baseline SD	Hedges g	Sample Size
Happiness	3.81	4.14	0.33	0.84	0.38	57
Gratitude	3.83	4.34	0.51	0.67	0.75	16

Sample size estimates were based on within-group changes in the Oxford Happiness Questionnaire, with a critical alpha of 0.05, and a power of 0.8, using a two-tailed t-test. Based on the data above, we would require 57 participants to detect a significant change in the Oxford Happiness Questionnaire. As we are recruiting a marginalised population, it is possible that the effect size following the intervention will be larger, and therefore we believe this reflects a conservative sample size estimate.

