## 2. SYNOPSIS

CanaCare is an interdisciplinary clinic and translational research study focused on health and wellness promotion for individuals who have experienced mental and physical health challenges due to a variety of circumstances, and are seeking assistance with lifestyle advice and choices which may lead to improved wellbeing, social integration, and engagement in their communities. The CanaCare team consists of a physician, accredited practising dietitians, accredited exercise physiologists, registered physiotherapists, registered psychologists, social workers, and a pharmacist. The clinic will utilise a person-centred approach for the delivery of a holistic assessment of each individual's physical and psychological health status and goals. The clinic team and the client will together structure a plan for reaching these goals which may include structured exercise (Linke et al, 2015; Hallgren et al, 2017, Lynch et al, 2013), nutritional changes (Opie et al, 2015; Teasdale et al, 2017), medication review, psychological support and counselling, control of substance use, referral to other health care practitioners for ongoing care or specialised tests, as well as behavioural support and ongoing feedback. Participants will be those individuals who have engaged with the Cana Communities not-for-profit organisation in any of its ongoing programs in NSW. The organisation supports individuals who have a wide variety of mental health conditions, disabilities, substance-use disorders, have been recently released from incarceration, those who have experienced loneliness and social isolation or disengagement, homelessness, domestic violence, refugees and those who have experienced trauma in its many forms.

Our primary outcome will be Happiness measured using the Oxford Happiness Scale, measured at baseline and 6 months. Secondary outcomes will include depressive symptoms, anxiety, sleep, quality of life, physical activity levels, dietary intake, body composition, exercise capacity, and functional mobility, as well as social integration/stability in domains of work, education, residential status, and relationships. (If there is no specific

scale, we will just ask the question about these areas before and after, to determine job status, living situation, etc).

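### The 57 in section 6.2 is a count of complete baseline/6-month pairs, but it is given as the participants required, with no loss allowance, and called conservative on effect size alone

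*Protocol*

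**What the plan says.** Section 6.2 takes two pre-post effects from a pilot trial in a non-clinical adult population. The table rows (pre mean, post mean, difference, baseline SD, Hedges g, sample size) are "Happiness 3.81 4.14 0.33 0.84 0.38 57" and "Gratitude 3.83 4.34 0.51 0.67 0.75 16". On the method it says: "Sample size estimates were based on within-group changes in the Oxford Happiness Questionnaire". The test settings are given as "with a critical alpha of 0.05, and a power of 0.8, using a two-tailed t-test". The smaller effect is adopted: "Based on the data above, we would require 57 participants to detect a significant change in the Oxford Happiness Questionnaire". The section closes by arguing, with the disadvantage of those to be recruited in mind, that "it is possible that the effect size following the intervention will be larger, and therefore we believe this reflects a conservative sample size estimate".

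The primary outcome is measured at baseline and 6 months (section 2), and the primary hypothesis concerns the score after 6 months (section 4). Sections 6.5 and 7.2 both provide for withdrawal at any time. According to section 2, the organisation from which participants come supports people with, among other circumstances, "substance-use disorders, have been recently released from incarceration, those who have experienced loneliness and social isolation or disengagement, homelessness". No expected loss to follow-up, inflation factor or separate enrolment target appears in section 6.2 or elsewhere in the protocol.

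**The concern.** A paired test of change uses only people measured at both times, so the number it returns is a number of completers. If 57 is also used as the enrolment number, losses over six months come straight out of the power.

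The word conservative makes this harder to see. The marginalised status of the population is used in one direction only, to suggest a larger effect. Its bearing on retention is not considered. A reader would conclude that 57 carries a margin, when no margin for missing 6-month data has been stated. At stake is how a non-significant primary result is read: it would be set against a stated power of 0.8 that may not have been available.

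**Working it through.** **Inputs.** From section 6.2: two-sided alpha 0.05, power 0.80, within-group t-test, g = 0.38 (adopted) and g = 0.75 (not adopted). Assumed here because the protocol gives no figure: loss of 10% to 40% by 6 months, and a pre-post correlation r of 0.3 to 0.7.

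**Formula.** For n complete pairs and a standardised change dz, the test has n − 1 degrees of freedom and noncentrality dz × √n. Power is the probability that a noncentral t variable falls outside ± the 97.5% point of the central t.

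**Step 1: reproduce the plan's figures**, using g directly as dz.
- dz = 0.38: n = 57 gives power 0.805 and n = 56 gives 0.798, so the smallest adequate n is 57. This matches.
- dz = 0.75: n = 16 gives power 0.801. This matches.

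So 57 is the smallest number of complete pairs that reaches 80%.

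**Step 2: power if 57 are enrolled**, dz = 0.38. Pairs are 57 × (1 − loss), to the nearest whole number. The detectable effect is the dz that gives 80% power with that many pairs. Enrolment to keep 57 pairs is 57/(1 − loss), rounded up.

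| Assumed loss | Pairs | Power | Detectable dz at 80% | Enrolment for 57 pairs |
|---|---|---|---|---|
| 0% | 57 | 0.805 | 0.38 | 57 |
| 10% | 51 | 0.758 | 0.40 | 64 |
| 20% | 46 | 0.713 | 0.42 | 72 |
| 30% | 40 | 0.649 | 0.45 | 82 |
| 40% | 34 | 0.576 | 0.50 | 95 |

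**Step 3: the correlation built into the calculation.** The table scales g by the baseline SD, whereas a paired test needs the SD of the change. With equal SDs at both times, dz = g / √(2(1 − r)). This equals g only when r = 0.5, so using 0.38 directly assumes r of about 0.5. At 20% loss (46 pairs):

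| r | dz | Power, 57 pairs | Power, 46 pairs |
|---|---|---|---|
| 0.3 | 0.38/√1.4 = 0.321 | 0.664 | 0.57 |
| 0.5 | 0.38/√1.0 = 0.380 | 0.805 | 0.71 |
| 0.6 | 0.38/√0.8 = 0.425 | 0.883 | 0.80 |
| 0.7 | 0.38/√0.6 = 0.491 | 0.953 | 0.90 |

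**Step 4: rounding of the effect.** The table's own 0.33/0.84 is 0.393. At that value 57 pairs give 0.830 and 53 pairs are enough for 80%, so about four losses (4/57 = 7%) would be absorbed.

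**The case against.** The strongest reply has four parts.

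- **The plan was cautious on effect size.** It shows two pilot effects and sizes on the smaller, giving 57 rather than 16. At 0.75, even 34 pairs would have about 99% power. This stands as a partial basis for the word conservative. But it is not the reason the protocol writes down, and it does not cover attrition if the effect is the 0.38 that was adopted.
- **57 may already mean completers.** The section says 57 are required; it does not say that enrolment stops there. This stands too. A reader might infer that the plan caps enrolment at 57, but the protocol sets no cap. The defect is that 57 is the only number given and its meaning is left open.
- **A higher correlation could absorb the losses.** At r = 0.7, 40 pairs still give about 86%. But at r = 0.3 even 57 complete pairs give only 66%. The protocol states no correlation, so this is not a planned margin.
- **Retention is supported, and 3-month data exist.** Sections 6.3 and 6.4 provide a linked volunteer with weekly calls at first, online follow-up and a repeated-measures analysis. These may reduce loss or recover some information, but the stated power rests on a simple pre-post t-test. They do make the 30% and 40% rows scenarios rather than forecasts.

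Two stronger readings are tempting and do not hold. One is that 57 is miscalculated; Step 1 shows that it is not. The other is that any loss at all breaks the power claim. One loss gives 0.798, which is immaterial, and on the unrounded effect the first few losses are absorbed.

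**Conclusion.** The concern holds as a missing planning allowance and an under-supported description, not as an arithmetic error. On the plan's own inputs, enrolling 57 stops delivering the stated 0.8 by a material amount once losses reach about 10% (0.758), and power falls to about 0.71 at 20%, 0.65 at 30% and 0.58 at 40%.

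These figures rest on loss rates that are assumed, a standardised change of exactly 0.38, and a pre-post correlation of about 0.5. The last assumption matters at least as much as attrition: at 20% loss, power runs from about 57% (r = 0.3) to 90% (r = 0.7). It would therefore be wrong to conclude that the trial is certainly underpowered. What the protocol supports is narrower: its power statement applies to 57 completers, it does not say so, and the word conservative implies a margin against loss that has not been provided.

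**What to change.** In section 6.2:

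1. Define 57 as the number of participants with both a baseline and a 6-month Oxford Happiness Questionnaire.
2. State the 6-month loss expected and its basis. For 57 enrolled, give the power (about 76%, 71%, 65% and 58% at 10%, 20%, 30% and 40% loss) or the matching detectable effect. Say that these figures assume a pre-post correlation of about 0.5, and show the range for other values.
3. Limit the word conservative to the choice of the smaller pilot effect, or remove it.

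Higher enrolment is optional. If the sponsor wishes to keep 57 pairs, the matching enrolment is 64, 72, 82 or 95 at 10%, 20%, 30% or 40% loss. The cost is a rewording of one section and a stated power that looks less favourable. Nothing in the intervention or the assessments changes.

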### **6.3 STUDY DESIGN**

Participants will be accompanied by a support person from the Cana Communities volunteer pool to the University of Sydney study site or will be supported by their support person to access one of the three online platforms (mentioned above) at a designated time. The participants will initially meet/talk to [name] [name] [study physician] to identify their primary goals/reasons for wanting to take part in the research program. Depending on what the participants identify as their primary (life) goal or aspiration/s, the physical and medical history assessment will focus on areas relevant to their goals.

Participants will then meet with one or more allied health practitioners for additional assessments to be completed. The interdisciplinary team will consist of accredited dietitians, accredited exercise physiologists, social workers, registered psychologists, registered physiotherapists and pharmacists. These assessments may include questionnaires, structured interviews, counselling sessions, body composition testing, nutritional assessments, fitness assessments and drug reviews.

A case conference will be held with all health practitioners involved in the participants' care. Subsequently, a case conference will be held with the team and the participants, with their support person present, to discuss their assessments, and how they relate to their goals. Through discussions with the participant, initial components of the Wellness program will be made. This may include exercise, dietary changes, mental health strategies such as mindfulness or meditation or cognitive behavioural therapy, or lessening of substance use, as appropriate. The care provided by CanaCare will be in addition to the usual supports provided by Cana Communities for effective reintegration into work, housing support, and social relationship building, among other offerings.

The Wellness program may take place across different sites including the University of Sydney Camperdown campus, Cana Communities sites around Sydney and Cana Farm in Orchard Hills and via the secure online platform chosen. Programs may be supervised or unsupervised, as appropriate, and will be interdisciplinary in nature. Where relevant, the study physician may make referrals to the participant's general practitioner, a psychiatrist or specialist.

Each participant will be linked with a Cana Communities volunteer from the community who will be his/her primary coordinator of care, depending on the most important or urgent goal or wellness need identified. This person will be responsible for follow-up by telephone on a weekly basis initially, to assist with the adoption of the Wellness program elements.

Follow-up will be planned for 3 months and 6 months to re-evaluate and re-set goals (either in-person or online). The participant will be accompanied/supported by their Cana support person if needed.

## 6.4 STATISTICAL ANALYSES

Descriptive data on participant characteristics and all outcomes will be generated using parametric and non-parametric summary statistics as appropriate to the distribution of the data. Relationships between variables of interest will be analysed via simple and multiple regression models or Spearman's correlation analyses as appropriate. Outcomes over time will be analysed through ANCOVA repeated measures with main effect of time and additional covariates as identified by review of the baseline data. Effect sizes will be generated for major primary and secondary outcomes of interest. Adherence to programmatic elements will be calculated and all adverse events, related and unrelated to study protocols will be tabulated. A p value of less than 0.05 will be accepted as a threshold of statistical significance. Clinical relevance of any changes observed in health status or behaviours will be determined by comparison to existing data on clinically meaningful changes in the relevant outcomes.

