##### **Primary Hypotheses**

Participation in the interdisciplinary CanaCare program, utilising a person-centred approach, will result in a significant improvement in the Oxford Happiness Score after 6 months.

Secondary aims of the study will be to assess the effect of the study on improvements in nutrition and health status, functional status, sleep quality, physical activity participation, neuropsychological outcomes (including depression, anxiety, self-esteem, and empathy), maximal aerobic capacity, muscle strength, physical performance, anthropometric parameters and body composition (including fat mass, fat free mass and bone mineral density).

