**Dietetics:**

Accredited practising dietitians (APDs) have undergone tertiary level training to provide expert nutrition and dietary advice to both individuals and groups on nutritional related matters (Dietitians Association of Australia [DAA], 2015). APDs within the CanaCare team will conduct assessments, perform diagnoses, implement interventions, as well as monitor and evaluate the therapeutic plan (DAA, 2018). They may provide education around healthy eating, shopping, and cooking, weight loss/weight gain, health with the management of a chronic health condition/s related to dietary patterns, and safe use of alcohol.

When working with individuals who have a mental health condition, APDs will utilise client-centred strategies for long-term dietetic and life-style self-management of relevant physical health outcomes, including goals related to long-term medication use (DAA, 2018).

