**Exercise Physiology:**

Accredited exercise physiologists (AEPs) have tertiary level training with the knowledge and skills to design, deliver and evaluate safe and effective exercise interventions for individuals who may have acute, sub-acute or chronic medical conditions, injuries or disabilities (Exercise & Sport Science Australia [ESSA], 2018). The overall aim of the AEP is to prevent, manage and assist individuals to regaining their optimal physical function, health or wellness (ESSA, 2018). If participants elect to see an AEP or exercise scientist, they will design an exercise intervention to improve strength and/or fitness, improve balance and reduce the risk of falls, improve body composition (decreasing fat mass and increasing muscle mass and increasing bone density), and better manage any chronic health condition/s they may have.

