## 9. OUTCOMES

Table 1 illustrates the CanaCare Clinic primary and secondary outcomes. All participants will complete the Oxford Happiness Questionnaire. Other outcome measures will be completed if they are relevant to the participant's goals.

Table 1. CanaCare Primary and Secondary Outcomes.

Primary Outcomes
1. Oxford Happiness Questionnaire score
Secondary Outcomes
1. Neuropsychological Outcomes 
 
1.1. Self-efficacy 
 
1.1.1. Ewart's Self Efficacy Scale
 
 
 
1.2. Empathy 
 
1.2.1. Toronto Empathy Scale
 
 
 
1.3. Quality of Life 
 
1.3.1. Short Form 36 Health Survey Questionnaire (SF-36)
 
 
 
1.4. Depression 
 
1.4.1. Patient Health Questionnaire-9 (PHQ-9)
 
1.4.2. Hamilton Depression Rating Scale (HAM-D)
 
 
 
1.5. Anxiety 
 
1.5.1. Generalised Anxiety Disorder 7-Item (GAD-7)
 
 
 
1.6. Post-traumatic Stress Disorder Symptoms 
 
1.6.1. Post-traumatic Stress Disorder Symptom Scale – Interview for DSM-5 (PSS-I-5)
 
 
 
1.7. Mindfulness 
 
1.7.1. Mindfulness Attention Awareness Scale
 
 
 
1.8. Experiential Avoidance 
 
1.8.1. Acceptance and Action Questionnaire (AAQ)
 
 
 

2. Aerobic Capacity 
 
2.1. Maximal aerobic capacity (VO2peak) 
 
2.1.1. Graded treadmill test to voluntary fatigue with indirect calorimetry
 
 
 

3. Muscular Strength 
 
3.1. One Repetition Maximum (1RM) (seated leg press, unilateral knee extension, chest press, and seated row)
 

4. Nutrition 
 
4.1. Short Form Food Frequency Questionnaire (SFFFQ)
 
4.2. CanaCare Dietary Questionnaire
 

5. Physical Performance 
 
5.1. 6-minute Walk Test (6MWT)
 
5.2. Short Physical Performance Battery
 
5.3. Balance (static and dynamic)
 

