
6. Anthropometry
 
6.1. Waist, upper-arm and calf circumference (cm)
 
6.2. Height (cm)
 
6.3. Weight (kg)

7. Body Composition
 
7.1. Whole body and regional lean and adipose tissue, Bone density in the lumbar spine and hip - Dual-energy X-ray absorptiometry (DXA)

8. Sleep Quality
 
8.1. Subjective sleep quality Pittsburgh Sleep Quality Index (PSQI)

9. Health Status
 
8.1 Past medical history Past medical diagnosis and symptoms (physical, mental or emotional), past treatments, medications, past falls.
 
8.2 Ongoing health status New medical diagnosis, new (or change) in symptoms, new (or change) in medications, falls, visits to health care practitioners. Gathered using a weekly health check questionnaire

10. Adherence to Intervention
 
10.1. All adverse events related and not related to the intervention. Gathered using weekly health status check and reporting of events throughout the study period.

11. Cognitive Function
 
11.1. Montreal Cognitive Assessment (MoCA) score

12. Haemodynamic Measures
 
12.1. Blood pressure Resting, orthostatic

13. Alcohol-related Outcomes
 
13.1. AUDIT-C

14. Physical Activity Levels
 
14.1. Subjective physical activity Paffenbarger Physical Activity Questionnaire Physical Activity Scale for the Elderly

15. Metabolic
 
15.1. The Australian Type 2 Diabetes Risk Assessment Tool (AUSRISK)

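### For weight and circumferences, the pooled main effect of time in section 6.4 does not match an aim of improvement when some participants may want to lose weight and others to gain it

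*Protocol*

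**What the plan says.** - **Aim.** Among the secondary aims, section 4 seeks improvement in "anthropometric parameters and body composition (including fat mass, fat free mass and bone mineral density").
- **Outcomes.** Table 1 in section 9 lists waist, upper-arm and calf circumference, height and weight (item 6), and DXA measures (item 7): "Whole body and regional lean and adipose tissue, Bone density in the lumbar spine and hip". No direction of success is attached to any of them.
- **Who is measured.** Everyone completes the Oxford Happiness Questionnaire. For the rest, "Other outcome measures will be completed if they are relevant to the participant's goals".
- **Programme content.** Of the dietitians, section 6.5.2 says: "They may provide education around healthy eating, shopping, and cooking, weight loss/weight gain". For those who choose exercise physiology, the same section describes a programme to "improve body composition (decreasing fat mass and increasing muscle mass and increasing bone density").
- **Goals.** Under section 6.3, the study physician identifies each participant's goals at the first meeting. Goals are re-set at 3 and 6 months.
- **Analysis.** Section 6.4 says: "Outcomes over time will be analysed through ANCOVA repeated measures with main effect of time". Further covariates are to be chosen after a look at the baseline values. The section also mentions regression or correlation between variables of interest, effect sizes, and a comparison of observed changes with published thresholds of clinical relevance. Goal direction is not named in any of these.

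**The concern.** A main effect of time asks whether the average of everyone measured has moved. That suits an outcome for which all participants want the same change. Weight and the circumferences need not be of that kind here, since the programme may help one person lose weight and another gain it, and both may be weighed because weight is relevant to their goals.

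The pooled mean then reflects the mix of goals as well as the success of the programme. A near-zero mean could arise although most people moved as they wished. A significant mean fall could include unwanted loss among people trying to gain. The second problem is one of meaning and does not go away with a larger sample.

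**Working it through.** **1. The plan's own figures.** Section 6.2 sizes the study on a within-group change in the Oxford Happiness Questionnaire, "with a critical alpha of 0.05, and a power of 0.8, using a two-tailed t-test". With the tabulated Hedges g as the standardised mean change and power taken from the non-central t distribution, g = 0.38 gives n = 57 and g = 0.75 gives n = 16. Both match the protocol's table. The same test is used below. The protocol makes no sample size calculation for weight.

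**2. Inputs for weight, all assumed.** The protocol gives no share of participants wanting gain, no SD of weight change and no number to be weighed. For illustration: average movement of 3 kg toward each person's own goal, SD of change within each direction 4 kg, a share *p* wanting gain, and either 30 or all 57 people weighed.

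**3. Formulae.**
- Pooled mean change = −3 × (1 − 2*p*) kg
- Pooled SD = √(4² + 4 × 3² × *p*(1 − *p*)) kg
- Standardised change *d* = |mean| / SD, entered in the two-sided paired t-test at 0.05

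For *p* = 0.30, the mean is −3 × 0.4 = −1.2 kg, the SD is √(16 + 36 × 0.21) = √23.56 = 4.85 kg, and *d* = 0.247.

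**4. Results for the pooled test.**

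| Share wanting gain | Mean (kg) | SD (kg) | *d* | Power, n = 30 | Power, n = 57 |
|---|---|---|---|---|---|
| 0% | −3.0 | 4.00 | 0.750 | 0.98 | >0.99 |
| 10% | −2.4 | 4.39 | 0.547 | 0.83 | 0.98 |
| 20% | −1.8 | 4.66 | 0.386 | 0.53 | 0.82 |
| 30% | −1.2 | 4.85 | 0.247 | 0.26 | 0.45 |
| 40% | −0.6 | 4.96 | 0.121 | 0.10 | 0.15 |
| 50% | 0.0 | 5.00 | 0 | 0.05 | 0.05 |

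In every row each group moves toward its goal by the same average amount; only the mix differs. At an even split the expected mean change is zero and power equals alpha.

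**5. A smaller effect.** If the movement toward goal is 0.38 SD, the effect used to size the study, power at n = 57 is 0.80, 0.60, 0.37, 0.19, 0.08 and 0.05 at 0, 10, 20, 30, 40 and 50% wanting gain.

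**6. Change signed toward each person's own goal.** The split then no longer matters. With the 3 kg and 4 kg assumptions, power is 0.98 at n = 30 and above 0.99 at n = 57. With 0.38 SD it is 0.52 and 0.80.

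**7. Would the stated covariates repair this?** A baseline covariate alongside a main effect of time still leaves one pooled mean change to be tested. The two directions separate only with a goal-by-time term or separate reporting, and section 6.4 states neither.

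**The case against.** **Detail for a statistical analysis plan.** Section 6.4 is a one-paragraph outline for all outcomes, and subgroup or responder summaries are commonly set out in a SAP, which is not at hand. This stands in part: the absence of a goal-based summary is not itself a fault. But the protocol does name a contrast, and for weight that contrast fits the stated aim poorly.

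**Thin textual basis.** A reader might infer that the dietetic programme sets goals in both directions. The protocol says only that dietitians may provide education on both, within a list of topics. How many participants will want to gain is unknown, and the number may be small.

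**Body composition.** A reader might infer that the whole body-composition domain is affected. The Exercise Physiology paragraph gives one desired direction each for fat, muscle and bone, so fat-free mass and bone density fall outside the point. Fat mass comes in only for participants with a weight-gain goal.

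**Other parts of section 6.4.** Regression on variables of interest or the clinical-relevance comparison could be made to take account of goals. Nothing in the text says that they will, but this is reason enough not to claim that the planned analyses cannot address the aim at all.

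**Small consequence.** With 10% wanting gain, power is still 0.83 at n = 30 and 0.98 at n = 57. These are a few items among fifteen secondary domains, and no power is claimed for them. This stands, and it limits the weight of the point.

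**Conclusion.** The point holds for weight and for waist, arm and calf circumference, and for fat mass only in participants with a weight-gain goal. For these, the pooled main effect of time does not measure improvement as the programme may define it, and opposite intended changes partly cancel.

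The size rests on assumptions: 3 kg average movement toward goal, SD 4 kg, and a loss-to-gain split that the protocol does not give. On those assumptions the loss of power is modest when gain goals are rare, large at about 30% (0.26 with 30 people, 0.45 with 57), and complete at an even split. A reader might conclude that the weight results will come out null; the documents do not support that, because the split is unknown.

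The Oxford Happiness Questionnaire has one desired direction, so the primary outcome and the sample size of 57 are unaffected. This is a cheap improvement to a secondary analysis, not a flaw that threatens the study.

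**What to change.** - **Baseline field.** Record each participant's intended weight direction at entry: lose, gain, or no weight goal. Keep that classification for analysis even when goals are re-set at 3 and 6 months, so that direction cannot be redefined after change has been seen.
- **Section 6.4.** For weight and circumferences, and for fat mass where a gain goal exists, report mean change with a 95% confidence interval by baseline direction. If the groups are small, use one analysis of change signed toward the baseline goal, with the no-goal group reported separately. Show the pooled mean as descriptive.
- **Unchanged.** Leave fat-free mass, bone density and the primary outcome as planned.

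**Cost.** One field, since goals are already elicited, and a sentence or two in section 6.4. The price is smaller groups and wider intervals: with 30 people weighed and 30% wanting gain, the groups are 9 and 21; at 10% they are 3 and 27, and the gain group is then descriptive only. Signed change keeps one larger group, but without a control arm, regression to the mean can favour both directions, so it should be read as movement toward the goal and not as proof that the programme caused it.
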